	
limiting toxicities occurring through Study Day 21 in the 8 actively treated patients in the current cohort (see Figure 2). In addition, pharmacokinetic and pharmacodynamic results will be reviewed to assess the appropriateness of the next planned dose and to guide revision of the next dose to be evaluated, if necessary.
 
Patients will undergo an up to 4-week Screening Period during which the ESA dose and parenteral iron doses must have been stable, as defined in the inclusion and exclusion criteria. All patients randomized will be continued on ESA and parenteral iron (if being given).
 
Patients meeting the entry criteria will generally be randomized on Day 1. The first dose of Study Drug will be administered during dialysis. Administration of the first dose of Study Drug will define Study Day 1. Additional visits will follow the schedule of events (see Appendix A: Schedule of Events). All subsequent Study Drug infusions will also be administered during dialysis and study visits will coincide with regularly scheduled dialysis treatments. Patients dropping out (i.e., prematurely discontinuing Study Drug treatment) for reasons unrelated to safety may be replaced in order to maintain the randomization ratio within each cohort.
 
Following the 12-week Treatment Period, patients will be followed for an additional 12 weeks for safety in the Safety Follow-Up Period. Patients will have completed their primary study participation at Week 24 (end of the Safety Follow-Up Period). Limited blood sampling will occur on Week 35 for anti-drug antibodies, pharmacokinetics, and IL-6 measurements as part of an Extended Follow-Up Period.

Study Periods:
	
The total study duration for an individual patient will be approximately 9 months, excluding the Screening Period.
 
Initial Screening Period: up to 2 weeks [Days -28 to -15]
 
 •Starts with the first date that Initial Screening procedures were performed. The first procedure also defines the initial screening visit date. 
Full Screening Period: up to 2 weeks [Days -14 through Day -1]
 
 •Starts with the date of the Week -2 Visit 
Treatment Period: 12 weeks [Week 1, Day 1 through Week 12]
 
Safety Follow-Up Period: 12 weeks [Weeks 13 through 24]
 
Extended Follow-Up Period: 10 weeks [Weeks 25 through 35]

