4.5 Patient Replacement

Patients dropping out (i.e., prematurely discontinuing Study Drug treatment) for reasons unrelated to safety may be replaced at the Sponsor’s discretion.

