11.3 General Statistical Considerations and Definitions

11.3.1 *General Statistical Methods*

All study-collected data will be summarized by treatment group using descriptive statistics, graphs, and/or raw data listings. Descriptive statistics for continuous variables will include number of patients (n), mean, standard deviation (SD), median, quartiles (Q1 and Q3), minimum (min) and maximum (max) values. Analysis of categorical variables will include frequency and percentage.

11.3.2 *Analysis Populations*

Intent-to-treat (ITT) analysis population: The ITT population will be defined as all randomized patients. Treatment classification will be based on the randomized treatment. This will be the primary population for the analyses of disposition and baseline data.

Pharmacodynamic analysis population: The pharmacodynamic population will be defined as all ITT patients who received their assigned Study Drug, had any pharmacodynamic assessments, and did not have major protocol violations. This will be the population for the pharmacodynamic analyses.

Per-protocol analysis population: The subset of the pharmacodynamics population that did not have a major protocol deviation, as defined in the SAP. The Per-Protocol analysis population will be used to perform the sensitivity analysis for the pharmacodynamics endpoints.

Pharmacokinetics analysis population: The PK population will be defined as all patients who have any valid samples measured for Study Drug levels. This will be used for PK analysis.

MTD analysis Population: The MTD analysis population will be defined as a subset of safety analysis population by excluding subjects replaced due to a non-safety reason. Treatment classification will be based on the actual treatment received. This population will be used for MTD and DLT analyses.

Safety analysis population: The safety population will consist of all patients randomized and treated with any amount of study medication (COR-001 or placebo). Treatment classification will be based on the actual treatment received. This population will be used for the safety analyses.

11.3.3 *Analysis Windows and Baseline*

If data are collected by visit, the data will be analyzed by visit based on the protocol-planned visits. If multiple records are collected for a visit, the latest record will be used for the summary for that visit.

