1.3 SUMMARY OF THE STUDY DESIGN

1.3.1 General Study Design and Plan

[figure not shown]
This is a randomized, double-blind, placebo-controlled trial designed to evaluate the safety, pharmacokinetics, and pharmacodynamic effects of multiple doses of COR-001 or placebo administered to sequential cohorts of hemodialysis patients.

Within each dosing cohort ten hemodialysis patients will be randomized to COR-001 or placebo at ratio of 8 to 2. Prior to dose escalation there will be a formal safety review by the Safety Review Committee (SRC). The SRC will specifically determine whether MTD has been exceeded based on protocol-defined DLT occurring through Study Day 21 in the 8 actively-treated patients in the current cohort (see Figure 1). In addition, pharmacokinetic and pharmacodynamic results will be reviewed to assess the appropriateness of the next planned dose and to guide revision of the next dose to be evaluated, if necessary. The planned doses are shown in Table 1. These doses may be adjusted based on accruing data; however, the maximum dose to be studied will not exceed the planned total dose in Cohort 4 (60 mg every 14 days [6 doses]).

A single interim analysis was planned to enable future program planning.

Patients will undergo an up to 4-week Screening Period. Those who meet the entry criteria will be randomized on Day 1 (a dialysis day) (or Day -1 with approval) and will receive the first dose of study drug during dialysis. Additional visits will follow the schedule of events (Appendix A, Section 15.1 of protocol). All subsequent study drug infusions will also be administered during dialysis and study visits will coincide with regularly scheduled dialysis treatments. Patients dropping out for reasons unrelated to safety may be replaced. Following the 12-week Treatment Period, patients will be followed for an additional 12 weeks for safety. The patients will have completed their primary study participation at Week 24 (end of the Safety Follow-Up Period). Sparse blood samples will be additionally collected on Week 35 for anti-drug antibodies, pharmacokinetics, and IL-6 measurements as part of an Extended Follow-Up Period.

Figure 1 Dose Escalation Schematic

The MTD assessment will be based on safety data from Weeks 1 to 3. If more than 2 of 8 active patients in a cohort experience a DLT, the MTD will be considered to have been exceeded.

¹If the MTD is not exceeded, dose escalation may continue.

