2.2 DEFINITIONS OF ANALYSIS SETS

The number of subjects entered, the number and the percentage of subjects included in each analysis set, and the number and the percentage of subjects excluded from each analysis set will be presented by dose group, treatment and overall.

Intent-to-treat (ITT) analysis population: The ITT analysis population will be defined as all randomized patients. Treatment classification will be based on the randomized treatment. This will be the primary population for the analyses of disposition and baseline data.

Pharmacodynamic analysis population: The pharmacodynamic population will be defined as all ITT patients who were treated with their assigned study drug treatment, had any pharmacodynamic assessments, and did not have certain important protocol deviations described below. This will be the population for the pharmacodynamic analyses.

- ≥ 2 Missed doses or ≥ 2 incorrect doses
- Important protocol deviations that are determined to significantly affect interpretation of PD endpoints, identified prior to unblinding of the study.
 - Minor departures from the ESA dosing guidelines in the protocol will not be considered major deviations.

For subjects who do not receive the assigned dose at any time during treatment, the dose will be defined as the highest dose received.

Pharmacokinetics analysis population: The PK population will be defined as all patients who have any valid samples measured for Study Drug levels. This will be used for PK analysis.

Safety analysis population: The safety analysis population will consist of all patients randomized and treated with any amount of study medication (COR-001 or placebo). Treatment classification will be based on the actual treatment received. This population will be used for the safety analyses.

MTD analysis Population: The MTD analysis population will be a subset of safety analysis population by excluding subjects replaced due to a non-safety reason. This population will be used for MTD and DLT analyses.

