5.2 EXTENT OF EXPOSURE

Study drug will be administered by infusion once every other week for 11 weeks (6 doses) for the planned treatment regimens in the protocol. Exposure will be summarized using the cumulative frequency and percentage of subjects receiving ≥ 1 dose, ≥ 2 doses, ... ≥ 5 doses, and 6 doses by treatment group. Descriptive statistics (number of subjects, mean, standard deviation, minimum, median, quartiles range, and maximum) for exposure will be summarized. In addition, the exposure (in days), defined as the date of the last dose of study drug – date of the first dose of study drug + 1 will be summarized. Exposure with respect to COR-001-01 blood levels will be described in the Pharmacokinetics and Pharmacokinetic-Pharmacodynamic Modeling Data Analysis Plan.

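### The MTD population excludes every patient replaced for a non-safety reason, even one with a complete 21-day DLT record or a DLT, and SAP section 8 names a different population for the same analysis

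*SAP*

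**What the plan says.** SAP 2.2 defines the set: "The MTD analysis population will be a subset of safety analysis population by excluding subjects replaced due to a non-safety reason". It adds: "This population will be used for MTD and DLT analyses". Protocol 11.3.2 carries the same exclusion: "The MTD analysis population will be defined as a subset of safety analysis population by excluding subjects replaced due to a non-safety reason". Neither text sets a condition on the day of departure, on completion of the DLT window, or on DLT status.

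The replacement rule in Protocol 4.5 reads: "Patients dropping out (i.e., prematurely discontinuing Study Drug treatment) for reasons unrelated to safety may be replaced". It leaves the choice to the sponsor and gives no cutoff date. The protocol synopsis gives the purpose: patients leaving "for reasons unrelated to safety may be replaced in order to maintain the randomization ratio" within each cohort.

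DLTs count over a shorter period. SAP 1.3.1 has the Safety Review Committee (SRC) judge the MTD from "protocol-defined DLT occurring through Study Day 21 in the 8 actively-treated patients in the current cohort". Dosing lasts much longer: six infusions over 11 weeks (SAP 5.2). Under Protocol 4.4 the MTD is exceeded when more than 2 of 8 active patients have a DLT, and a single Grade 4 or 5 DLT blocks escalation.

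SAP section 8 opens by placing all safety analyses on the safety population. That section contains the DLT counts (8.1) and the table of events meeting DLT criteria on Days 1 to 21 (8.3).

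**The concern.** The exclusion depends on whether a patient was replaced. What matters for a DLT rate is whether the patient could be assessed for DLT. The two differ for anyone who leaves after Day 21. A patient who stops in Week 6 has a complete DLT record, yet leaves the MTD set if the sponsor replaces them.

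A patient with a DLT can also be lost. A DLT does not by itself end treatment: the individual stopping rule in Protocol 4.4 names only severe infusion-type reactions. Protocol 4.3 lists withdrawal of consent and organ transplantation among the reasons for stopping drug. A patient could have a DLT, continue, leave later for such a reason, be replaced, and disappear from the count. Protocol 4.3 also asks patients who stop drug to complete follow-up, so the excluded records will often be usable.

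Characterization of the MTD is the primary safety endpoint, and DLT frequency is the first secondary safety endpoint (SAP 1.2.1 and 1.2.2). MTD status also decides which cohorts enter the pooled pharmacodynamic analyses (SAP 1.2.3 and 7). A reader of SAP 2.2 and a reader of SAP section 8 could report different DLT counts for the same cohort.

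**Working it through.** **Inputs.** 8 active patients per cohort and an expected DLT rate of 25% (Protocol 11.1, SAP 1.3.2). The MTD is exceeded at 3 or more DLTs (Protocol 4.4). DLTs count through Day 21 (SAP 1.3.1). The documents give no number of replacements, so one replaced active patient per cohort is an assumption. DLTs are taken as independent between patients.

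**The plan's own figures.** With X ~ Binomial(8, 0.25):
- P(X ≥ 2) = 0.6329 (stated: greater than 63%).
- P(X ≥ 1) = 0.8999 (stated: 90%).

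Both reproduce. The decision rule needs 3 or more:
- P(X = 2) = 28 × 0.25² × 0.75⁶ = 0.311.
- P(X = 3) = 56 × 0.25³ × 0.75⁵ = 0.208.
- P(X ≥ 3) = 0.321.

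**Replacement unrelated to DLT status.** One evaluable patient, chosen without regard to DLT, is exchanged for a new one.
- From 3 DLTs to 2: the lost patient is one of the three (3/8) and the new one has no DLT (0.75). 0.208 × 3/8 × 0.75 = 0.058.
- From 2 DLTs to 3: the lost patient is one of the six without a DLT (6/8) and the new one has a DLT (0.25). 0.311 × 6/8 × 0.25 = 0.058.

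The flows are equal. The new set is again Binomial(8, 0.25), and P(X ≥ 3) stays at 0.321. A complete record has been lost, but the rule is not shifted.

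**Replacement that depends on DLT status.** Two extremes bound one exchange.
- The replaced patient is always one with a DLT, if there is one. A cohort at 3 falls to 2 of the remaining 7 and returns to 3 only if the new patient has a DLT. P(flag) = P(X ≥ 4) + 0.25 × P(X = 3) = (0.321 − 0.208) + 0.25 × 0.208 = 0.166 (computed from unrounded terms).
- The replaced patient never has a DLT. P(flag) = 0.321 + 0.25 × P(X = 2) = 0.321 + 0.078 = 0.399.

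These are limits. They do not predict what will happen.

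**Keeping the evaluable patient.** If the count of 3 or more is left unchanged:

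| Evaluable active patients | P(3 or more DLTs) at 25% |
|---|---|
| 8 | 0.321 |
| 9 | 0.399 |
| 10 | 0.474 |

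**The two population statements.** SAP 2.2 assigns MTD and DLT analyses to the MTD set. SAP section 8 assigns all safety analyses, including 8.1, to the safety population. For a replaced patient with a DLT, the first gives a count one lower than the second. Both cannot govern the same table.

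**The case against.** The rule has a sensible aim. The rationale given with Amendment 2 is to protect the denominator used for MTD determination. Replacement is optional, and patients who leave for safety reasons stay in the MTD set. The harmful case is narrow: a patient with a DLT, a later departure classed as unrelated to safety, and a decision by the sponsor to replace. All of this stands, and it limits how often the problem would arise. It does not supply the missing condition on evaluability.

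Three stronger readings are tempting, and the documents do not support them.

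First, a reader might count only the moves from 3 DLTs to 2 and infer that the rule makes the MTD too lenient. Under the same assumption, moves from 2 to 3 are equally likely. A directional bias needs a link between DLT status and departure or replacement. The documents do not establish one, although a discretionary replacement with no requirement to ignore DLT status does not rule it out.

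Second, a reader might infer that escalation decisions are corrupted. The SRC reviews a cohort once all its patients have completed 21 days or had their last visit (SAP 10.1), so a patient replaced after that review has already been counted. The live decision is exposed only if an early enrollee is replaced while later patients are still completing Day 21. Even then the SRC applies its own judgment, and SAP 2.1 does not say which population its tables use.

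Third, a reader might infer that the event vanishes. It does not: the patient stays in the safety population and in the adverse event tables.

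**Conclusion.** The point holds as a defect in the definition of the analysis set. As written, SAP 2.2 and Protocol 11.3.2 can remove a complete DLT record, or an actual DLT, from the final MTD and DLT-frequency analyses. SAP 2.2 and SAP section 8 also contradict each other on the population for the primary safety analysis.

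The size depends on facts that the documents do not give. If replacement is independent of DLT status, there is no shift in the flag probability of 0.321 at a 25% rate, only lost information. If it depends fully on DLT status, one exchange could take that probability anywhere from 0.166 to 0.399. A lost Grade 4 or 5 DLT would likewise disappear from the final count. These figures assume one replaced active patient per cohort and independent DLTs. The effect falls mainly on the final analysis. It reaches the live decision only through a replacement before the cohort's review.

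**What to change.** 1. In SAP 2.2 and Protocol 11.3.2, define the MTD population as all treated patients who had a DLT through Day 21 or completed Day 21. Exclude only those replaced for a non-safety reason before Day 21 without a DLT. State also where a patient belongs who leaves before Day 21 without a DLT and is not replaced; the present rule keeps that patient in.
2. Reconcile SAP 2.2 with SAP section 8 so that one population is named for the MTD and DLT analyses, including the tables in 8.1 and 8.3.
3. Have the sponsor state how the more-than-2-of-8 rule is read when more than 8 active patients in a cohort are evaluable.

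The cost is a few sentences across the two documents and no new data. There is a statistical price to declare: if the count of 3 or more is left unchanged, the flag probability at a 25% rate rises from 0.321 with eight evaluable patients to 0.399 with nine. That change in operating characteristics should be stated whichever reading the sponsor adopts.

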2.3 TIME WINDOWS FOR ANALYSIS

If data are collected by visit, the data will be analyzed by visit based on the protocol-planned visits. If multiple records are collected for a visit, the latest record will be used for the summary for that visit. Unless otherwise specified, baseline is defined as the last non-missing value prior to initiation of study drug. Early termination visit will be mapped to the post-baseline scheduled visit. After mapping, if there is more than one visit in the same window, the scheduled visit will be used if available. If there is no scheduled visit in the same window, the mapped visit closer to the target assessment day will be used. If more than one visit has the equal distance to the target day, then the later one will be used. The unscheduled visit will not be included in the by-visit summary, but will be included in the outlier analysis.

The observational period for the study will start from informed consent and end with study completion (see [Section 3.1](#) for the definition of study completion). Any event occurring after the defined observational period, even if collected on the CRF, may not be included in the summary statistical analysis. However, all data, including that reported after the defined observational period, will be included in the patient data listings.

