The observational period for the study will start from informed consent and end with study completion (see [Section 4.6](#)) for the definition of study completion). Any event occurring after the defined observational period, even if collected on the CRF, may not be included in the planned statistical analysis. However, all data, including that reported after the defined observational period, will be included in the patient data listings.

For evaluations that are collected at multiple occasions prior to initiation of Study Drug, the latest evaluation will be considered the "Baseline" evaluation for analysis, unless otherwise specified.

11.3.4 *Missing Data Handling*

Unless otherwise specified, missing data will not be imputed and will be excluded from the associated analysis.

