If dialysis is still ongoing and the sample is being drawn through the arterial blood line/sample port, obtain the sample in a manner that minimizes possible recirculation in the dialysis access. See Study Reference Manual for recommendations. Alternatively, the sample may be drawn through a peripheral needle stick.

[c] 4 [+ 2] hours after completing the infusion, whenever feasible (e.g., first shift patients)

[d] Within 10 minutes after completing dialysis. Please see recommendations for blood drawing in section (b) above.

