7.1 PRIMARY PHARMACODYNAMIC ANALYSIS

Endpoints:

The primary pharmacodynamic efficacy of COR-001 compared to placebo will be assessed by evaluating the following:

- Change from baseline (mean of Full Screening and Day 1 values) in hsCRP to Week 4 between treatment groups
 - The Day 29 value will be used for this analysis, reflecting at least 4 weeks of completed treatment. To ensure comparability to the post-baseline value, only the pre-dialysis Screening values will be used for the baseline.

Analysis Set:

Pharmacodynamic analysis population

Method:

Number of patients (n), mean, standard deviation (SD), median, quartiles (Q1 and Q3), minimum (min) and maximum (max) values for the observed value and change from baseline will be reported. The difference in changes (COR-001 - Placebo) will be presented. An analysis of covariance (ANCOVA) model will be used for this purpose with dose (specific active dose or placebo pooled) as a factor and baseline value as a covariate. The least square means for each dose, the least square mean differences from placebo along with the associated 95% confidence intervals (CIs) and p-values will be presented.

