7.2 SECONDARY PHARMACODYNAMIC ANALYSES

Endpoints:

1. Change from baseline (mean of Full Screening and Day 1 values) in hsCRP to the mean of Weeks 10-12
2. Change from baseline (mean of Full Screening and Day 1 values) in SAA to Week 4 between treatment groups
3. Change from baseline (mean of Full Screening and Day 1 values) in SAA to the mean of Weeks 10-12
4. Change from baseline (mean of Full Screening and Day 1 values) in the free IL-6 to Week 4 between treatment groups
5. Change from baseline (mean of Full Screening and Day 1 values) in Hemoglobin to Week 4
6. Change from baseline (mean of Full Screening and Day 1 values) in Hemoglobin to Week 10-12
7. Change from baseline (mean of Full Screening and Day 1 values) in Hemoglobin to Week 10-12, excluding hemoglobin values following a change in the total weekly ESA dose. A change is defined as the first time when the ESA weekly dose goes up by >25% or down by >25% relative to the previous week's dose.
8. Change from baseline (weekly mean of Full Screening) in ERI to the mean of Weeks 9-12 and Weeks 10-12

- a. The Screening ERI is defined as the ERI used to qualify the patient for the study per Inclusion Criterion #14
9. Change from baseline (mean of Screening and Day 1 values) in TSAT to Week 4
10. Change from baseline (mean of Full Screening and Day 1 values) in TSAT to Weeks 10-12
11. Change from baseline (mean of Screening and Day 1 values) in the CHr to Week 4
12. Change from baseline (mean of Full Screening and Day 1 values) in the CHr to Weeks 10-12
13. Change from baseline (mean of Full Screening and Day 1 values) in serum pre-albumin to the mean of Weeks 10-12
14. Change from baseline (mean of Full Screening and Day 1 values) in serum albumin to Week 12

Analysis Set:

Pharmacodynamic analysis population

Method:

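### The latest-record rule, read literally, puts post-infusion and post-dialysis hsCRP and pre-albumin samples into the Weeks 10-12 endpoints against a wholly pre-dialysis baseline, and leaves the Day 1 free IL-6 baseline sample undefined

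*SAP*

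**What the plan says.** SAP 2.3 sets the record-selection rule: "If multiple records are collected for a visit, the latest record will be used for the summary for that visit". Protocol 11.3.3 carries the same sentence. Neither section distinguishes repeats of one assessment from samples planned at different times within a visit.

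Protocol Appendix A plans such samples, under four codes: [a] shortly before dialysis, [b] just after the infusion, [c] 4 to 6 hours after the infusion where practical, and [d], defined as "Within 10 minutes after completing dialysis".

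SAP 7.2 lists the Weeks 10-12 endpoints for hsCRP and pre-albumin, the latter as "Change from baseline (mean of Full Screening and Day 1 values) in serum pre-albumin to the mean of Weeks 10-12", without naming a sample. The only statement about sample type for these laboratory markers is in SAP 7.1, under the primary hsCRP endpoint: "To ensure comparability to the post-baseline value, only the pre-dialysis Screening values will be used for the baseline".

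For baseline in general, SAP 2.3 says: "Unless otherwise specified, baseline is defined as the last non-missing value prior to initiation of study drug". The free IL-6 endpoint in SAP 7.2 has its own baseline, the average of Full Screening and Day 1 values, and does not say whether the Day 1 value is pre-dose.

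**The concern.** The 7.1 safeguard acts on the wrong side of the comparison. Screening hsCRP is drawn only before dialysis, so restricting it to pre-dialysis values changes nothing. The mixed samples are post-baseline, where the latest-record rule decides and favors the later draw.

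Fluid removal during dialysis can concentrate plasma proteins. A change computed from a post-dialysis value and a pre-dialysis baseline then moves upward with no drug effect. For pre-albumin that looks like improvement within an arm; for hsCRP it hides part of a fall. Because [c] is drawn only where practical, the Day 71 value would be [c] in some patients and [b] in others, which adds variability.

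For free IL-6 the issue is which Day 1 sample is meant. A post-dose value would be suppressed in active patients only, so the active-arm baseline would be lowered and the ANCOVA covariate would itself be affected by treatment.

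**Working it through.** The plan gives no figure of its own on this point. The check applies the rule to the schedule and then does simple arithmetic.

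**Step 1: record selected (codes from Appendix A).**

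| Visit | hsCRP | Pre-albumin | Latest record |
|---|---|---|---|
| Week -2, Week -1, Day 1 | a | a | a |
| Days 3, 5, 8 | a, d | a, d | d |
| Day 15 | a, b | a, b | b |
| Days 22, 29, 36, 43, 57 | a | a | a |
| Day 50 | d | d | d (only sample) |
| Day 64 | a | none | a |
| Day 71 | a, b, c | a, b, c | c, or b if c not drawn |
| Day 75 | a, d | a, d | d |
| Day 78 | a | a | a |

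**Step 2: share f of non-pre-dialysis values in the Weeks 10-12 mean.**
- By sampling day: hsCRP (Days 64, 71, 75, 78) 2/4 = 50%; pre-albumin (Days 71, 75, 78) 2/3 = 67%.
- If Week 11 contributes once: hsCRP 1/3; pre-albumin 1/2.

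**Step 3: within-arm shift.** Let h be the proportional rise in concentration in the later samples. With a stable marker, the Weeks 10-12 mean rises by f x h. Assume h = 5% to 20%.
- hsCRP by sampling day: 0.50 x 5% = 2.5% to 0.50 x 20% = 10%.
- Pre-albumin by sampling day: 0.667 x 5% = 3.3% to 0.667 x 20% = 13.3%.
- Week 11 counted once: hsCRP 1.7% to 6.7%; pre-albumin 2.5% to 10%.

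These are upper bounds, because they give Day 71 the full post-dialysis effect. A [b] sample may be drawn while dialysis is still running, and [c] comes hours after the infusion.

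**Step 4: between-arm difference.** Let m_A and m_P be the true arm means over Weeks 10-12. If h is proportional and equal in both arms, the difference becomes (m_A - m_P) x (1 + f x h). With no drug effect and equal baselines it stays at zero; a real difference is rescaled by the few percent in Step 3.

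**Step 5: free IL-6, only if a post-dose Day 1 value were used.** Day 1 is coded a, b, c. Let B be the pre-drug level and assume 90% suppression both after the Day 1 dose and at Week 4; protocol 3.5.2 sets inhibition above 90% as the level needed for effect.
- Averaging Week -2, Week -1 and Day 1: baseline (B + B + 0.10B)/3 = 0.70B; raw change 0.10B - 0.70B = -0.60B instead of -0.90B, an understatement of 0.30/0.90 = one third.
- Averaging the Screening mean with Day 1: baseline (B + 0.10B)/2 = 0.55B; raw change -0.45B, an understatement of one half.

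The SAP estimates the effect by ANCOVA, not by raw change. In the three-value case the adjusted difference is -0.90B + s x 0.30B, where s is the pooled slope of the Week 4 value on baseline. Take 48 active and 12 placebo patients (six cohorts at 8:2) and values that track B exactly. Then s = (48 x 0.70 x 0.10 + 12)/(48 x 0.70 x 0.70 + 12) = 15.36/35.52 = 0.43. The understatement is 0.43 x 0.30/0.90 = about 14%. Random variation in the baseline would reduce s and this figure.

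**The case against.** The intent seems clear. SAP 7.1 seeks comparability with a post-baseline value that it evidently takes to be pre-dialysis, and the SAP separates pre- and post-dialysis results for vital signs and cardiac markers. Multiple records could reasonably mean repeats of one assessment. That is a fair account of intent, but no sentence applies it to hsCRP or pre-albumin, and a programmer following SAP 2.3 literally would produce the mismatch.

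Four stronger readings are tempting, and the documents do not support them:

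- **That the primary hsCRP result is affected.** It is not. SAP 7.1 says: "The Day 29 value will be used for this analysis, reflecting at least 4 weeks of completed treatment". Day 29 has only an [a] sample, as has Day 22. SAA is drawn only at [a] throughout.
- **That the plan prescribes a drug-contaminated free IL-6 baseline.** It does not. The SAP 2.3 default is pre-drug, and protocol 11.3.3 also builds on pre-drug values: "For evaluations that are collected at multiple occasions prior to initiation of Study Drug, the latest evaluation will be considered" as baseline. The endpoint's own definition displaces the default without saying which Day 1 sample is meant, so the text is ambiguous. Free IL-6 is also secondary only in the SAP; protocol Amendment 3 made it exploratory.
- **That the treatment effect on free IL-6 would be understated by a third.** That figure applies to the raw change, not to the planned ANCOVA estimate.
- **That the pre-albumin comparison would show a false benefit.** Both arms share one sampling scheme, so the shift largely cancels between them.

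The Day 50 post-dialysis values come from the schedule and not from this rule.

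**Conclusion.** The point holds for secondary and exploratory pharmacodynamic results. Read literally, the rule compares mixed post-infusion and post-dialysis hsCRP and pre-albumin values with a purely pre-dialysis baseline in the Weeks 10-12 endpoints, and would do the same in by-visit summaries on Days 3, 5, 8 and 15. Within-arm changes shift upward by at most about 2% to 13%. That size rests on the assumed 5% to 20% hemoconcentration and on how Week 11 is counted. The between-arm difference is little biased if hemoconcentration is similar in the two arms; some variability is added, which the documents do not allow one to quantify.

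For free IL-6 the finding is an unresolved definition, with consequences for the active-arm baseline and the ANCOVA covariate only if a post-dose Day 1 value is used. This should be corrected, but it does not threaten the primary analyses.

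**What to change.** State the following in SAP 2.3 and 7.2, and align protocol 11.3.3:

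- Endpoints and by-visit change summaries for hsCRP, pre-albumin and free and total IL-6 use the pre-dialysis, pre-infusion [a] sample.
- The Day 1 value in any baseline is the pre-dose sample.
- The latest-record rule applies only to repeats of the same nominal time point.
- Samples [b], [c] and [d] are kept for PK-PD modeling and for describing pre- to post-dialysis change.
- Visits with only a [d] sample are labeled as post-dialysis: Day 50 for hsCRP, pre-albumin and IL-6, and Day 8 for IL-6.

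The cost is a few sentences and one programming filter, best settled before Database Lock 1, when the SAP locks these endpoint data. The [d]-only visits drop out of the over-time change summaries. An [a] sample is scheduled on every day that feeds the affected Week 4 and Weeks 10-12 endpoints, so no endpoint value is lost.
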